The secondary objective of this study is to assess the safety and tolerability of aramchol administered orally in subjects with hepatic impairment.

STUDY DESIGN:

This is a Phase 1, multicenter, open-label, 2-part, single- and multiple-dose study designed to assess the effect of hepatic insufficiency on the PK of aramchol.

Each part of the study will consist of a screening period, a check-in day, a treatment period, and an end-of-study (EOS) visit.

In Part 1 (single-dose), up to 48 subjects are planned: 8 subjects each in the mild (Cohort A), moderate (Cohort B), and severe (Cohort C) hepatic impairment cohorts and 8 to 24 healthy control subjects with normal hepatic function (Cohort D). Enrollment of 8 subjects with mild hepatic impairment (Cohort A) will proceed only if there is evidence of reduced clearance of aramchol in Cohort B. At screening, subjects will be assigned to a study cohort according to the Child-Pugh classification system as follows:

Cohort	Hepatic Condition	Child-Pugh Grade	Number of Subjects
A ^(a)	Mild impairment	Class A (Score of 5 to 6)	8
B	Moderate impairment	Class B (Score of 7 to 9)	8
C	Severe impairment	Class C (Score of 10 to 15)	8
D	Healthy (control)	—	8 to 24

^(a) Enrollment of subjects into Cohort A will only proceed if there is evidence of reduced clearance of aramchol in Cohort B.

Healthy control subjects (Cohort D) will be matched with hepatically impaired subjects (Cohorts A, B, and C) according to gender, age (± 10 years), and body mass index ($\pm 20\%$).

Safety data and PK profiles of aramchol from at least 4 subjects with moderate hepatic impairment (Cohort B) will be obtained and reviewed while enrollment to this cohort continues. These 4 subjects in Cohort B must demonstrate satisfactory safety (no serious adverse events [AEs] or severe AEs related to aramchol) and PK results for up to 4 days after dosing before enrollment of subjects with severe hepatic impairment (Cohort C) is initiated. Two subjects with severe hepatic impairment must demonstrate satisfactory safety and tolerability (no serious AEs or severe AEs related to aramchol) for up to 4 days after dosing before the remaining subjects with severe hepatic impairment may be dosed.

Enrollment of subjects into Cohort A (mild hepatic impairment) will proceed only if there is evidence of reduced clearance of aramchol in the first 4 subjects in Cohort B (moderate hepatic impairment), defined as a reduction in apparent total oral clearance (CL/F) of greater than 30% compared with values in historical healthy control subjects.

In Part 2, a cohort of at least 8 subjects comprising of mild and moderate or moderate and severe hepatic impairment subjects will be administered aramchol as multiple doses to obtain the PK profile of aramchol at steady state. A decision on the severity of hepatic impairment of subjects to participate in Part 2 (multiple-dose) will be made by the sponsor based on the available safety and PK results from Part 1 (single-dose).

Healthy control subjects will be matched with the hepatically impaired subjects according to gender, age (± 10 years), and body mass index ($\pm 20\%$).

Single Dose (Part 1):

On Day 1, subjects will receive a single oral dose of 600 mg aramchol administered with water in the morning, after an overnight fast of at least 10 hours, and approximately 30 minutes after consuming a standardized breakfast. Subjects will remain fasted except for water for 2 hours after dosing. During the study, subjects may consume water on an ad libitum basis. Hepatically impaired subjects will receive a diet standardized for hepatic impairment and healthy control subjects will receive a similar diet.

Serial blood samples for PK analysis of aramchol concentrations in plasma will be collected before dosing (0 hour) and up to 168 hours for healthy subjects and 240 hours for hepatically impaired subjects after administration of aramchol.

Subjects will be confined to the clinical site from Day -1 until discharge on Day 8 for healthy control subjects and on Day 11 for hepatically impaired subjects. The duration of the study, excluding screening, is approximately 23 days.

Multiple Dose (Part 2):

Multiple dosing will involve twice daily (approximately 12 hours apart) oral administration of aramchol for 11 days with a single AM dose on Day 12 to achieve steady state. The dosage will not exceed 300 mg twice daily but may be adjusted to give lower exposure depending on review of available data on any reduction in clearance associated with hepatic impairment seen with single doses in Part 1. Subjects will consume a standardized meal 30 minutes prior to the AM and PM doses of aramchol. Subjects will remain fasted except for water for 2 hours after dosing. During the study, subjects may consume water on an ad libitum basis. Hepatically impaired subjects will receive a diet standardized for hepatic impairment and healthy control subjects will receive a similar diet.

Blood samples for analysis of aramchol concentrations in plasma will be collected before the AM dose on Days 1, 4, 8, 9, 10, 11, and 12 and at intervals to 12 hours after the AM dose on Day 12. Samples of plasma will also be stored for analysis of metabolites pending results of a mass balance study.

Subjects will be confined to the clinical site from Day –1 until discharge on Day 13. The duration of the study, excluding screening, is approximately 28 days.

STUDY POPULATION:

Inclusion Criteria:

Each subject must meet all of the following criteria to be enrolled in this study:

1. The subject is male or female 18 to 79 years of age, inclusive.
2. The subject has a body mass index of 19 to 40 kg/m², inclusive, at screening.
3. Females of childbearing potential must practice a highly effective method of contraception throughout the study period and for 1 month after treatment discontinuation. Highly effective methods are defined as those that can achieve a failure rate of less than 1% per year when used consistently and correctly. Such methods, in accordance with the recommendations of the Clinical Trial Facilitation Group Working Group on Contraception include: hormonal contraception associated with inhibition of ovulation, intrauterine device, intrauterine hormonal-releasing system, bilateral tubal occlusion, vasectomized partner, and sexual abstinence. All female subjects must have a negative pregnancy test at screening and before the first dose of study drug.
4. Male subjects with female partners of childbearing potential must be vasectomized, be willing to use an acceptable method of birth control, or practice abstinence during the study.
5. The subject has a resting pulse rate of ≥ 40 and < 100 beats per minute with no clinically significant deviation as judged by the investigator.
6. The subject has a QT interval corrected for heart rate using Fridericia's formula of < 500 msec.
7. The subject agrees to comply with all protocol requirements.
8. The subject is able to provide written informed consent.

Additional Inclusion Criteria for Healthy Subjects Only (Cohort D):

9. The subject has normal hepatic function.
10. The subject has a resting blood pressure of 90 to 150 mm Hg (systolic) and 50 to 100 mm Hg (diastolic).
11. The subject is judged by the investigator to be in good general health, as determined by medical history, clinical laboratory assessments, vital sign measurements, 12-lead electrocardiogram (ECG) results, and physical examination findings.

Additional Inclusion Criteria for Subjects With Hepatic Impairment Only (Cohorts A, B, and C):

12. The subject has cirrhosis with evidence of impaired liver function. The etiology of the cirrhosis may be alcoholic, autoimmune, nonalcoholic steatohepatitis, or chronic viral hepatitis type B or C.
13. The subject has chronic (more than 6 months) and stable hepatic impairment (ie, no acute episodes of illness within 30 days before screening due to deterioration of hepatic

function) as assessed by a Child-Pugh classification score of mild (5 to 6 points), moderate (7 to 9 points), or severe (10 to 15 points).

14. The subject has a resting blood pressure of 90 to 155 mm Hg (systolic) and 50 to 100 mm Hg (diastolic).
15. The subject is judged by the investigator to be in good general health, as determined by medical history, clinical laboratory assessments, vital sign measurements, 12-lead ECG results, and physical examination findings, except for findings that, as judged by the investigator, are consistent with the subject's hepatic impairment or other stable concomitant medical conditions.

Exclusion Criteria:

Subjects meeting any of the following criteria will be excluded from the study:

1. The subject has a history or clinical manifestations of a significant neurological, renal, cardiovascular, gastrointestinal, pulmonary, hematologic, immunologic, or psychiatric disease that would preclude study participation, as judged by the investigator.
2. The subject has a positive test result for human immunodeficiency virus type 1 or 2 antibodies at screening.
3. The subject has a history of drug abuse within 3 months before screening.
4. The subject has a history of alcoholism within 3 months before screening, or excessive alcohol consumption (regular alcohol intake >15 units per week) (1 unit is equal to approximately ½ pint [200 mL] of beer, 1 small glass [100 mL] of wine, or 1 measure [25 mL] of spirits).
5. The subject smokes >10 cigarettes daily and is unwilling to reduce to ≤5 daily from the time of screening through the last PK sample.
6. The subject is unable or unwilling to abstain from alcohol, caffeine, xanthine-containing beverages or food (eg, coffee, tea, chocolate, and caffeinated sodas, colas), grapefruit, grapefruit juice, Seville oranges, or products containing any of these, from 48 hours prior to study drug dosing until discharge.
7. The subject is involved in strenuous activity or contact sports within 24 hours of the first dose of study drug or during the study.
8. The subject has donated blood or blood products >450 mL within 3 months before the first dose of study drug.
9. The subject has a presence or history of relevant drug and/or food allergies (ie, allergy to aramchol, cholic acid, or any excipients, or any significant food allergy).
10. The subject has received study drug in another investigational study within 30 days of dosing.
11. In the opinion of the investigator, the subject is not suitable for entry into the study.

Additional Exclusion Criteria for Healthy Subjects Only (Cohort D):

12. The subject has clinically significant findings at screening including history, physical examination, ECG, or laboratory values.
13. The subject has used an herbal remedy (including St John's wort) known to interfere with liver enzymes during the 28 days before dosing with the study drug.

14. The subject has a past history of surgery or a medical condition that might affect absorption of medicines (hernia repair is acceptable).
15. The subject has a positive test result for hepatitis B surface antigen or antibodies to hepatitis C virus.
16. The subject has used any prescription (excluding hormonal birth control and hormone replacement therapy) or over-the-counter medications (except paracetamol [up to 2 grams per day]), including herbal or nutritional supplements, within 14 days before the first dose of study drug and throughout the study.
17. The subject has a positive test result for drugs of abuse or alcohol at screening or before the first dose of study drug.

Additional Exclusion Criteria for Subjects With Hepatic Impairment Only (Cohorts A, B, and C):

18. The subject has a current >Grade 1 (mild) encephalopathy. Subjects with a history of Grade 3 or 4 encephalopathy that have responded to treatment with medicines such as lactulose, rifaximin, or neomycin may be included with the subject receiving the point score for Grade 3 or 4 encephalopathy.
19. The subject has clinically demonstrated massive tense ascites. Subjects with a history of moderate or severe ascites that have responded to diuretics may be included with the subject receiving the higher score.
20. The subject has esophageal varices that have caused hemorrhage within a period of 8 weeks prior to dosing or are considered of high risk for hemorrhage.
21. The subject has the following types of liver disease: primary biliary cirrhosis, sclerosing cholangitis, hepatocellular carcinoma, cardiac cirrhosis, hemochromatosis, Wilson's disease, other genetic causes of liver disease.
22. The subject has clinically significant impairment of renal function (eCLcr <45 mL/min) as calculated by the Cockcroft-Gault equation.
23. The subject has a hemoglobin <8.5 mg/dL or platelets <30,000/ μ L.
24. The subject has fluctuating or rapidly deteriorating hepatic function, as indicated by recent history or worsening of clinical (ie, abdominal pain, nausea, vomiting, anorexia, or fever) and/or laboratory signs of hepatic impairment, as judged by the investigator.
25. The subject has evidence of acute viral hepatitis within 30 days before dosing with study drug.
26. The subject has evidence of hepatorenal syndrome.
27. The subject has used any prescription (excluding hormonal birth control and hormone replacement therapy) or over-the-counter medications, including herbal or nutritional supplements, within 14 days before the first dose of study drug and throughout the study, except those essential for the management of hepatic impairment or the treatment of stable concomitant medical conditions, as judged by the investigator. The dose of an approved medication must remain stable from 7 days before study drug dosing and throughout the study.

28. The subject has a positive test result for drugs of abuse (except positive test results associated with prescription medications that have been reviewed and approved by the investigator) at screening or before the first dose of study drug.

STUDY TREATMENTS:

Single Dose (Part 1):

Aramchol will be administered as a single oral dose of 600 mg (2×300 -mg tablets) in the morning on Day 1 with water approximately 30 minutes after a standardized breakfast.

Multiple Dose (Part 2):

Aramchol will be administered as an oral dose that will not exceed 300 mg twice daily (approximately 12 hours apart) for 11 days and a single AM dose on Day 12 with water approximately 30 minutes after a standardized meal.

STUDY PROCEDURES:

Pharmacokinetic Assessments and Endpoints:

Single Dose (Part 1):

Blood samples for analysis of concentrations of aramchol and its metabolites in plasma will be collected at the following time points: before dosing (0 hour) and at 1, 2, 3, 4, 5, 6, 8, 10, 12, 14, 18, 24, 48, 72, 96, 120, 144, 168, 192, and 240 hours (the last 2 time points are for hepatically impaired subjects only) after administration of aramchol.

The following plasma PK parameters will be calculated as endpoints for aramchol using actual sampling times rather than scheduled sampling times:

- Area under the plasma concentration versus time curve (AUC) from time 0 to the last quantifiable concentration (AUC_{0-t})
- AUC from time 0 extrapolated to infinity (AUC_{0-inf})
- Maximum observed plasma concentration (C_{max})
- Time to reach maximum observed plasma concentration (T_{max})
- Time to the first measurable plasma concentration (T_{lag})
- Apparent terminal elimination half-life ($t_{1/2}$)
- Apparent oral clearance (CL/F)
- Apparent volume of distribution (V_z/F)
- Elimination rate constant (k_e)

Multiple Dose (Part 2):

Blood samples for analysis of concentrations of aramchol and its metabolites in plasma will be collected before the AM dose on Days 1, 4, 8, 9, 10, 11, and 12 and at the following times after the AM dose on Day 12: 1, 2, 3, 4, 5, 6, 8, 10, and 12 hours.

The following plasma PK parameters on Day 12 will be calculated as endpoints for aramchol using actual sampling times rather than scheduled sampling times (if conducted):

- AUC from time 0 to the dosing interval tau at steady state ($AUC_{0-tau, ss}$)

- Maximum observed plasma concentration at steady state ($C_{max, ss}$)
- Time to reach maximum observed plasma concentration at steady state ($T_{max, ss}$)
- Minimum observed plasma concentration at steady state ($C_{min, ss}$)
- Time of minimum observed plasma concentration at steady state ($T_{min, ss}$)
- Average plasma concentration at steady state ($C_{avg, ss}$)

Time to reach steady state will also be estimated graphically by assessing trough plasma concentrations (ie, pre-AM dosing on Days 1, 4, 8, 9, 10, 11, and 12) over 12 days of administration.

Safety Assessments and Endpoints:

Safety and tolerability will be assessed by the following endpoints: monitoring and recording of AEs, clinical laboratory test results (hematology, coagulation, serum chemistry, and urinalysis), vital sign measurements, 12-lead ECG results, and physical examination findings.

STATISTICAL ANALYSIS PLANS:

Sample Size:

For Part 1, up to 48 subjects are planned: 8 subjects each in the mild (Cohort A), moderate (Cohort B), and severe (Cohort C) hepatic impairment groups, and 8 to 24 healthy control subjects with normal hepatic function (Cohort D). For Part 2, at least 8 subjects with mild and moderate or moderate and severe hepatic impairment and up to 8 healthy control subjects with normal hepatic function are planned. The sample size was chosen for this study based on clinical and practical considerations and not on a formal statistical power calculation. The US Food and Drug Administration Guidance for Industry, Pharmacokinetics in Patients With Impaired Hepatic Function: Study Design, Data Analysis, and Impact on Dosing and Labeling, was used as a guide to select the sample size, which is considered sufficient to adequately assess the safety and PK profiles of aramchol.

In the event of early withdrawals or discontinuations, subjects may be replaced at the discretion of the investigator, and after consultation with the medical monitor and sponsor if the number of completers will be less than 6 subjects in any cohort.

Analysis Sets:

The PK population will include subjects who receive at least 1 dose of aramchol and have sufficient concentration data to support accurate estimation of at least 1 PK parameter. In Part 1, subjects who experience vomiting within 6 hours after dosing will be excluded from the PK analysis.

The safety population will include all subjects who receive at least 1 dose of aramchol.

Pharmacokinetic Analyses:

Plasma concentrations will be listed and summarized descriptively (number of subjects, arithmetic mean, standard deviation [SD], coefficient of variation [CV], minimum, median, and maximum). Plasma concentration versus actual time profiles for each subject will be presented graphically. The mean plasma concentration versus scheduled time profiles will be presented graphically.

Pharmacokinetic parameters derived from plasma concentration data using noncompartmental methods will be summarized by hepatic group using descriptive statistics (number of subjects, arithmetic mean, SD, CV, minimum, median, and maximum). Geometric mean and geometric CV will also be calculated for AUCs and C_{max} . The AUC_{0-t} , AUC_{0-inf} , and C_{max} values may also be expressed in terms of unbound drug concentrations.

An analysis of variance (ANOVA) model will be performed on the natural logarithms of AUC_{0-t} , AUC_{0-inf} , and C_{max} to calculate the ratio of geometric means and its 90% confidence interval between subjects with hepatic impairment and the corresponding healthy control subjects, as appropriate. The ANOVA model will include hepatic group (normal matching mild, mild, normal matching moderate, moderate, normal matching severe, and severe, where applicable) as a fixed effect.

For AUC_{0-t} , AUC_{0-inf} , and C_{max} , a linear regression model will be performed on the natural logarithms of AUC_{0-t} , AUC_{0-inf} , and C_{max} as dependent variables and each of the following natural-log-transformed hepatic function estimates as independent variables: Child-Pugh classification score (in subjects with hepatic impairment only), baseline serum bilirubin, serum albumin, and prothrombin time. The regression coefficients representing the relationship between the PK parameters and the hepatic function estimates will be estimated together with their 90% confidence intervals from the regression model.

Sensitivity analyses may be conducted to investigate the potential impact of imbalance existing across hepatic impairment groups in the distribution of the baseline covariates used in subject matching (eg, body weight) and, if data suggest, appreciable differences in PK exposure (AUC_{0-t} , AUC_{0-inf} , and C_{max}) across different values of the same baseline covariate.

Detailed descriptions of the analyses in this study will be presented in the statistical analysis plan.

Safety Analyses:

Adverse events will be coded by preferred term and system organ class using the latest version of the Medical Dictionary for Regulatory Activities. All AE data will be presented in a data listing. Treatment-emergent AEs will be summarized by hepatic condition and overall, as well as by severity and relationship to study drug. Serious AEs and AEs leading to early discontinuation will also be presented in data listings.

Actual values and changes from baseline for clinical laboratory test results, vital sign measurements, and 12-lead ECG results will be summarized by hepatic condition at each time point using descriptive statistics (number of subjects, mean, SD, minimum, median, and maximum). Shift tables will be generated for clinical laboratory test results. Clinical laboratory test results, vital sign measurements, 12-lead ECG results, and physical examination findings will be presented in data listings.

DATE OF PROTOCOL: 14 October 2019

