1. INTRODUCTION

1.1 BACKGROUND

Aramchol is a novel conjugate of cholic acid (bile acid) and arachidic acid (saturated fatty acid), linked by a stable amide group. It is in development for treatment of nonalcoholic steatohepatitis (NASH) and fibrosis. Aramchol affects stearoyl coenzyme A desaturase 1, a key liver enzyme involved in regulating lipid metabolism. In animal models of NASH, it reduces steatosis, ballooning, inflammation, and fibrosis by down-regulation of stearoyl coenzyme A desaturase 1 expression in hepatocytes and hepatic stellate cells.

Aramchol is highly lipophilic and pharmacokinetic (PK) studies in humans show that plasma concentrations increase less than proportionally to dose due to poor absorption. Its mean terminal phase half-life ($t_{1/2}$) is approximately 3 days but most of the drug is cleared with a $t_{1/2}$ of about 35 hours and steady state on repeat dosing is achieved within 7 to 10 days. Aramchol is secreted in bile and is excreted in feces. [REDACTED]

[REDACTED]

[REDACTED]

[REDACTED] Two

Phase 2 clinical studies have been completed including a placebo-controlled study in which subjects with NASH were treated for 52-weeks. Significantly more subjects who received aramchol 600 mg daily showed NASH resolution without worsening of fibrosis and a larger proportion of subjects showed at least a 1-point improvement in fibrosis score without worsening of steatohepatitis.

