1.3 RATIONALE FOR DOSE SELECTION

A single oral dose of 600 mg aramchol in Part 1 and multiple oral doses not to exceed 300 mg aramchol twice daily for 11 days and a single AM dose on Day 12 in Part 2 will be evaluated in this study based on the recommendations provided in the US Food and Drug Administration (FDA) Guidance for Industry, Pharmacokinetics in Patients with Impaired Hepatic Function: Study Design, Data Analysis, and Impact on Dosing and Labeling (DHHS 2003). Though single doses up to 900 mg have been studied in healthy subjects and tolerated well, the single dose of 600 mg represents the highest dose likely to be used and was the daily dose administered in the Phase 2b study. The multiple dose of 300 mg twice daily has been well tolerated by healthy subjects for 10 days and is the dose to be taken daily by subjects participating in a Phase 3 clinical trial.

The duration of multiple dosing is based on the apparent plasma elimination half-life of about 35 hours and time taken to reach steady state of about 7 days in healthy subjects. A duration of 10 days was chosen to ensure steady state has been achieved by all the healthy subjects and an additional 2 days is considered appropriate for subjects with hepatic impairment owing to the possibility of reduced clearance in this population.

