5. STUDY TREATMENTS

5.1 TREATMENTS ADMINISTERED

All doses of study drug will be administered by mouth with 240 mL of room temperature water. During the study, subjects may consume water on an ad libitum basis.

Hepatically impaired subjects will receive a diet standardized for hepatic impairment and healthy control subjects will receive a similar diet. Subjects should receive these meals at the same time during each part of the study.

Single Dose (Part 1):

On Day 1, all subjects will receive a single oral dose of 600 mg (2 × 300-mg tablets) aramchol in the morning, after an overnight fast of at least 10 hours and approximately 30 minutes after a standardized breakfast.

Multiple Dose (Part 2):

Starting on Day 1, all subjects will receive an oral dose of aramchol that will not exceed 300 mg twice daily (approximately 12 hours apart) for 11 days and a single AM dose on Day 12 approximately 30 minutes after a standardized meal. The dose may be adjusted to give lower exposure depending on the review of available data on any reduction in clearance associated with hepatic impairment seen with single doses in Part 1.

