5.5 TREATMENT COMPLIANCE

All doses of the study drug will be administered in the clinical site under direct observation of site personnel and recorded in the eCRF. Clinic personnel will confirm that the subject has received the entire dose of study drug.

The date and time of study drug dosing will be recorded on the appropriate page in the eCRF. If a subject is not administered study drug, the reason for the missed dose will be recorded.

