6.1 PHARMACOKINETIC ASSESSMENTS AND ENDPOINTS

Single Dose (Part 1):

Blood samples for analysis of concentrations of aramchol and its metabolites in plasma will be collected at the following time points: before dosing (0 hour) and at 1, 2, 3, 4, 5, 6, 8, 10, 12, 14, 18, 24, 48, 72, 96, 120, 144, 168, 192, and 240 hours (the last 2 time points are for hepatically impaired subjects only) after administration of aramchol. Acceptable time deviations are ± 5 minutes for 0 to 4 hours, ± 10 minutes for >4 to 8 hours, ± 15 minutes for >8 to 24 hours, ± 30 minutes for >24 to 72 hours, and ± 60 minutes for >72 hours to 240 hours.

The following plasma PK parameters will be calculated as endpoints for aramchol using actual sampling times rather than scheduled sampling times:

- AUC from time 0 to the last quantifiable concentration (AUC_{0-t})

- AUC from time 0 extrapolated to infinity (AUC_{0-inf})
- Maximum observed plasma concentration (C_{max})
- Time to reach maximum observed plasma concentration (T_{max})
- Time to the first measurable plasma concentration (T_{lag})
- Apparent terminal elimination half-life ($t_{1/2}$)
- Apparent oral clearance (CL/F)
- Apparent volume of distribution (V_z/F)
- Elimination rate constant (k_e)

Multiple Dose (Part 2):

Blood samples for analysis of concentrations of aramchol and its metabolites in plasma will be collected before the AM dose on Days 1, 4, 8, 9, 10, 11, and 12 and at the following times after the AM dose on Day 12: 1, 2, 3, 4, 5, 6, 8, 10, and 12 hours. Acceptable time deviations are ± 5 minutes for 0 to 4 hours, ± 10 minutes for >4 to 8 hours, and ± 15 minutes for >8 to 12 hours.

The following plasma PK parameters on Day 12 will be calculated as endpoints for aramchol using actual sampling times rather than scheduled sampling times (if conducted):

- AUC from time 0 to the dosing interval tau at steady state ($AUC_{0-tau, ss}$)
- Maximum observed plasma concentration at steady state ($C_{max, ss}$)
- Time to reach maximum observed plasma concentration at steady state ($T_{max, ss}$)
- Minimum observed plasma concentration at steady state ($C_{min, ss}$)
- Time of minimum observed plasma concentration at steady state ($T_{min, ss}$)
- Average plasma concentration at steady state ($C_{avg, ss}$)

Time to reach steady state will also be estimated graphically by assessing trough plasma concentrations (ie, pre-AM dosing on Days 1, 4, 8, 9, 10, 11, and 12) over 12 days of administration.

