7.2 ANALYSIS SETS

The analysis populations are as follows:

- The PK population will include subjects who receive at least 1 dose of aramchol and have sufficient concentration data to support accurate estimation of at least 1 PK parameter. In

Part 1, subjects who experience vomiting within 6 hours after study drug dosing will be excluded from the PK analysis.

- The safety population will include all subjects who receive at least 1 dose of aramchol.

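### The PK population rule excludes vomited doses in Part 1 only, so Part 2 subjects who lose doses on or just before Day 12 can enter the steady-state summaries

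*Combined protocol and SAP*

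**What the plan says.** The analysis-set text appears in the synopsis (Analysis Sets) and in Section 7.2. Entry to the PK population, for both parts, requires at least one dose and that the subject "have sufficient concentration data to support accurate estimation of at least 1 PK parameter". The only exclusion tied to dosing is: "In Part 1, subjects who experience vomiting within 6 hours after dosing will be excluded from the PK analysis".

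The Part 2 regimen in Section 5.1 is a dose "that will not exceed 300 mg twice daily (approximately 12 hours apart) for 11 days and a single AM dose on Day 12". That is 2 × 11 + 1 = 23 doses.

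Section 6.1 takes all the listed Part 2 parameters from one profile: "The following plasma PK parameters on Day 12 will be calculated as endpoints for aramchol using actual sampling times rather than scheduled sampling times". All of them carry the steady-state label. The protocol also says "Time to reach steady state will also be estimated graphically by assessing trough plasma concentrations", but attaches no exclusion criterion to that plot.

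Section 5.5 provides for observed dosing and adds "If a subject is not administered study drug, the reason for the missed dose will be recorded". It gives no analysis consequence. Section 7.4 deals with missing and BLQ concentrations, not with missed doses.

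**The concern.** Part 2 exists to obtain the steady-state profile. Section 1.3 adds two days of dosing so that impaired subjects, who may clear the drug more slowly, reach steady state. A subject who loses a dose on Day 11, or vomits the Day 12 morning dose, can still give every sample from 0 to 12 hours. That subject meets the population definition, and the resulting AUC is reported as a steady-state value. The AUC is accurately computed, but it is the AUC of an interrupted regimen.

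Every late loss pushes the Day 12 exposure down. If the losses fell mainly on impaired subjects, the comparison with healthy controls would hide part of any rise in exposure, which is what the study is looking for. The study is also open-label, so without a written rule the decision to keep or drop such a profile may be made after the concentrations are known.

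**Working it through.** **Inputs from the documents.** Section 1.3 gives an "apparent plasma elimination half-life of about 35 hours and time taken to reach steady state of about 7 days in healthy subjects". Section 1.1 says that the mean terminal half-life "is approximately 3 days but most of the drug is cleared with a" half-life of about 35 hours, so 72 h serves as the slow case. Doses are 12 h apart, there are 23 of them, and Part 2 has at least 8 impaired subjects.

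**Assumptions.** Linear one-compartment kinetics; nothing absorbed from a lost dose; absorption rate ka from 0.15 per hour to instantaneous. The documents give no ka.

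**Step 1: the protocol's own figure.** Fraction of steady state after time t is 1 − 2^(−t/half-life). At 35 h:
- 7 days (168 h): 1 − 2^(−168/35) = 96.4%
- 10 days (240 h): 99.1%
- before the Day 12 dose (264 h): 99.5%

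The stated 7 days is therefore consistent with 35 h.

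**Step 2: contribution of each dose to Day 12 AUC0-tau.** With k = ln 2/half-life, the share of a single dose's total AUC accrued by time t is

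F(t) = 1 − [ka·e^(−kt) − k·e^(−ka·t)]/(ka − k),

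which becomes 1 − e^(−kt) with instantaneous absorption. A dose given a hours before the Day 12 morning dose contributes F(a + 12) − F(a). The 23 contributions add up to F(276). The loss is the sum of the lost doses' contributions divided by F(276).

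With instantaneous absorption at 35 h, k = 0.0198 per hour and F(276) = 0.9958:
- Day 12 AM: (1 − 0.7885)/0.9958 = 21.2%
- Day 11 PM: (0.7885 − 0.6217)/0.9958 = 16.8%
- Both Day 11 doses: (0.7885 − 0.4902)/0.9958 = 30.0%

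Across the range of ka:

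| Dose(s) lost | Loss at 35 h | Loss at 72 h |
|---|---|---|
| Day 12 AM | 12-21% | 6-12% |
| Day 11 PM | 17-18% | 10-11% |
| Both Day 11 doses | 30-32% | about 20% |
| All four Day 10-11 doses | 49-53% | 35-37% |
| Day 8 AM | 3-4% | about 5% |
| Day 5 AM | about 0.8-0.9% | 2.3-2.5% |
| Day 4 AM | about 0.5% | about 2% |

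Cavg,ss is AUC0-tau divided by 12 h, so it falls by the same percentage. For a lost Day 12 AM dose at 35 h, Cmax,ss falls by 9-18% (ka 0.3 to 2.0 per hour). The pre-dose trough is unchanged, so the trough plot would not reveal that case.

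**Step 3: cohort geometric mean, one affected subject in 8.** The fall is 1 − (1 − loss)^(1/8). At 35 h:
- Day 12 AM: 1 − (0.883)^(1/8) = 1.5% to 1 − (0.788)^(1/8) = 2.9%
- Day 11 PM: about 2.3-2.4%
- Both Day 11 doses: 1 − (0.700)^(1/8) = 4.4% to 1 − (0.679)^(1/8) = 4.7%
- All four Day 10-11 doses: about 8-9%

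**The case against.** **Missed doses are unlikely and would be seen.** Part 2 subjects are confined from Day −1 to Day 13, and site staff watch each dose and confirm it was taken in full (Section 5.5). A missed dose would be a protocol deviation, and important deviations go into the study report (Sections 9.2.1 and 9.2.3.2.2). Noncompliance can lead to withdrawal (Section 4.4.1). This stands: losing all four Day 10-11 doses is remote, and vomiting is the main route. But these provisions record or flag the event. None decides whether the profile enters the summary, and confirming that a dose was received does not show it was retained.

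**The steady-state parameters are not in the named model.** The ANOVA and regression in Section 7.3.1 are specified for AUC0-t, AUC0-inf and Cmax. The Part 2 parameters are explicitly planned only for descriptive summary, alongside individual plots and listings. This stands and limits the damage.

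**Detail is deferred.** Section 7.3 points to a separate SAP that was not supplied and may contain a Part 2 rule. That cannot be checked. The protocol does state the Part 1 rule itself, and as written it admits the Part 2 profiles.

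**Different rules by part can be legitimate.** In Part 1 vomiting may lose the only dose. In Part 2 an early loss has largely washed out by Day 12, as the Day 4 and Day 5 figures show. So the difference between the parts is not an error in itself; the gap is confined to the last few doses.

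**The losses are upper values.** Vomiting some hours after dosing may lose only part of the dose. This also stands.

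A reader might infer that lost doses are commoner in moderate or severe impairment, so that exposure is understated in the impaired group alone. The documents give no rates by group. Exclusion 24 lists vomiting among the signs of worsening hepatic function, but it does so to keep such subjects out.

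**Conclusion.** The gap is real, and no provision in the supplied text closes it. Under Section 7.2 and the synopsis, a Part 2 subject who loses the Day 12 morning dose or doses shortly before it can enter summaries labelled steady state. At a 35 h half-life with nothing absorbed from the lost dose, that subject's AUC0-tau is understated by roughly 12-32% when one or both of the last doses are lost. The cohort geometric mean moves by only about 1.5-5% if one subject in 8 is affected. At 72 h the effects are smaller.

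The conclusion is conditional on late losses actually occurring. It should not be read as saying that Part 2 will understate exposure, or that the bias runs against the impaired group: that direction follows only if the losses concentrate there. Separately, at a 72 h half-life Day 12 AUC0-tau would reach only about 93% of steady state with every dose retained, and a lost-dose rule would not change that.

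**What to change.** In Section 7.2 and the synopsis, add that a Part 2 subject's Day 12 parameters are left out of the main steady-state summary in either of two cases:
- the Day 12 morning dose was vomited within the window already used for Part 1;
- a dose in a short pre-specified period before Day 12 was missed, or was vomited within that window.

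Days 10-11 are a reasonable example of that period, because losses there change AUC0-tau materially. Requiring about 7 days of complete dosing would be too strict: it would drop a subject for a Day 5 loss worth under 1% of AUC0-tau at 35 h. List the excluded profiles and show a sensitivity summary that includes them. Put the same rule in the separate SAP, and settle it before Part 2 concentrations are reviewed.

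The cost is a sentence or two and one extra summary. Doses are observed and their times recorded, and vomiting is captured as an adverse event, so no new procedure is needed. This is an analysis-set rule and changes no dosing. The drawback is that a cohort of about 8 may lose a subject from the main summary. Because the exclusion follows a post-dose event it could introduce some selection, which is why the sensitivity summary matters.
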